13.3 Informed Consent Process

13.3.1 Consent/Accent and Other Informational Documents Provided to Subjects

The investigator or his/her representative will explain the nature of the study to the subject or his/her legally authorized representative and answer all questions regarding the study. Subjects will be required to sign and date a study consent form prior to any study-related procedures are performed if they meet eligibility requirements of the protocol and wish to participate in the trial. If applicable, it will be provided in a certified translation of the local language.

- Subjects must be informed that their participation is voluntary. Subjects or their legally authorized representative [defined as an individual or judicial or other body authorized under applicable law to consent on behalf of a prospective subject to the subject's participation in the procedure(s) involved in the research] will be required to sign a statement of informed consent that meets the requirements of 21 CFR 50, local regulations, ICH guidelines, Health Insurance Portability and Accountability Act requirements, where applicable, and the IRB/IEC or study center.
- The medical record must include a statement that written informed consent was obtained before the subject was enrolled in the study and the date the written consent was obtained. The authorized person obtaining the informed consent must also sign the ICF.

- Subjects must be re-consented to the most current version of the ICF(s) while receiving study treatment.
- A copy of the signed and dated ICF(s) must be provided to the subject or the subject's legally authorized representative.
- Subjects who are rescreened are required to sign a new ICF.

The ICF may contain a separate section or a separate ICF may be used for optional exploratory research. The investigator or authorized designee will explain to each subject the objectives of the exploratory research. Subjects will be informed that they are free to refuse to participate and may withdraw their consent at any time and for any reason during the study period.

13.3.2 Consent Procedures and Documentation

Informed consent is a process that is initiated prior to the individual's agreeing to participate in the study and continues throughout the individual's study participation. Extensive discussion of risks and possible benefits of participation will be provided to the subjects. Consent forms will be IRB/IEC approved and the subject and/or the legally authorized representative will be asked to read and review the document. All subjects will receive a verbal explanation in terms suited to their comprehension of the purposes, procedures, and potential risks of the study and of their rights as research subjects. Subjects will have the opportunity to carefully review the written consent form and ask questions prior to signing. The subjects should have the opportunity to discuss the study with their surrogates or think about it prior to agreeing to participate. The subject and/or the subject's legally authorized representative will sign and date the informed consent document prior to any procedures being done specifically for the study. The subject may withdraw consent at any time throughout the course of the trial. A copy of the signed and dated informed consent document will be given to the subject or the subject's legally authorized representative for their records. The rights and welfare of the subjects will be protected by emphasizing to them that the quality of their medical care will not be adversely affected if they decline to participate in this study.

13.4 Subject and Data Confidentiality

Subject confidentiality is strictly held in trust by the participating investigators, their staff, and the Sponsor(s) and their agents. This confidentiality is extended to cover testing of biological samples in addition to the clinical information relating to subjects. Therefore, the study protocol, study documentation, data, and all other study-related information generated will be held in strict confidence. No information concerning the study, or the data will be released to any unauthorized third party without prior written approval of the Sponsor.

The study monitor, auditors, other authorized representatives of the Sponsor including the contract research organization (CRO), if applicable, representatives of the IRB/IEC or the Sponsor supplying study product, the Federal government or its designee and applicable regulatory authorities will be granted direct access to the study subjects' original medical records (including but not limited to office, clinic, hospital, or pharmacy records), all documents required to be maintained by the investigator, for verification of clinical trial procedures and/or data, without violating the confidentiality of the subjects, to the extent permitted by the law and regulations.

All documents will be stored safely in a secure location to protect confidentiality. On all trial-specific documents, other than the signed consent, the subject will be referred to by the trial subject identification number/code, not by name. At the end of the study, all records will continue to be kept in a secure location for as long a period as dictated by local IRB/IEC and Institutional regulations.

Study subject research data, which is for purposes of statistical analysis and scientific reporting, will be transmitted to and stored a Sponsor location. This will not include the subject's contact or identifying information. Rather, individual subjects and their research data will be identified by a unique study identification number. The study data entry and study management systems used by research staff at the clinical sites and by authorized representatives of the Sponsor will be secured and password protected. At the end of the study, all study databases will be de-identified and archived at a Sponsor location.

13.4.1 Research Use of Stored Human Samples, Specimens, or Specimen Data

Intended Use: Samples and data collected under this protocol may be used to study the PK and PD of SL-172154, PLD, and/or MIRV, as well as biomarkers associated with ovarian cancer and/or the mechanism of action of each study drug. Research may include the study of genomic alterations and changes in the TME which may correlate with drug safety or efficacy.

Storage: Access to stored samples will be limited to specified study personnel/vendor personnel. Samples will be identified by unique subject identification (ID) codes. Samples and data will be stored using subject ID assigned by the Sponsor and investigators. An individual subject may choose to withdraw their consent at any time; however, the Sponsor will retain all data previously analyzed and will retain and continue to use any data or biological samples collected prior to the consent withdrawal, unless the subject specifically requests disposal of their samples.

14. DATA HANDLING AND RECORD KEEPING

14.1 Communication and Data Dissemination Plan

During the study while subjects are receiving study treatment in dose escalation as well as dose expansion cohorts, SMC meetings will be held to review relevant data with the investigators or designees (see Section 7.8 for details). These meetings will be held once a month (or more frequently if required) during dose escalation, provided subjects have been enrolled and data are available to be reviewed, to share safety data and communicate results of ongoing analyses. All available safety, PK, PD, and clinical outcome data for all subjects at the time of the scheduled SMC Meeting will be reviewed and summarized. Attendees of SMC meetings will include, but not be limited to clinical investigators (or designees), the Sponsor Medical Monitor and Statistician. The SMC will operate in accordance with the SMC charter which will define roles and accountabilities as well as the process for safety review and meeting frequency.

The Sponsor will remain in constant contact with the clinical sites during the enrollment period to ensure that cohort enrollment during the dose escalation of this study is completed as per protocol. All dose escalation or safety decisions made by the SMC will be documented in writing with copies maintained at each site and the Trial Master File at the Contract Research Organization.

14.2 Data Collection and Management Responsibilities

An eCRF will be used to record all subject data specified by this protocol. The eCRF must be completed by designated and trained study personnel. The eCRF will be electronically signed by the Principal Investigator or a Sub-investigator listed on the Form FDA 1572 (or equivalent). Data collection is the responsibility of the clinical trial staff at the site under the supervision of the site investigator. The investigator is responsible for ensuring the accuracy, completeness, legibility, and timeliness of the data reported. All source documents should be completed in a neat, legible manner to ensure accurate interpretation of data. Source documents may include but are not limited to, study progress notes, e-mail correspondence, computer printouts, laboratory data, and drug accountability records.

Data reported in the eCRF derived from source documents should be consistent with the source documents or the discrepancies should be explained and captured in a progress note and maintained in the subject's official electronic study record.

Clinical data (including, but not limited to AEs, concomitant medications, and expected ARs data) and clinical laboratory data will be entered into the study database, a 21 CFR Part 11-compliant data capture system provided by the Sponsor. The data system includes password protection and internal quality checks, such as automatic range checks, to identify data that appear inconsistent, incomplete, or inaccurate. Clinical data will be entered into an electronic data capture system directly from the source documents.

Study data will be entered into eCRFs at the study site. Prior to database lock, programmed computer edit checks and manual checks will be performed to check for discrepancies and reasonableness of the data. All issues resulting from these checks are to be resolved as quickly as possible with clarification from study sites.

14.3 Study Records Retention

The Sponsor follows US regulations and ICH guidelines in its retention policy.

US IND regulations (21 CFR 312.62c) require that records and documents pertaining to the conduct of this study and the distribution of investigational drug(s) including eCRFs, consent forms, laboratory test results, and medication inventory records be kept on file by the Principal Investigator for 2 years following the date a marketing application is approved for the drug for the indication for which it is being studied. If no application is to be filed or if the application is not approved for such indication, these records must be kept until 2 years after the investigation has been discontinued and regulatory authorities (i.e., FDA, Health Canada, European Medicines Agency, etc.) have been notified. ICH guidelines indicate that study documents should be retained until at least 2 years after the last approval of a marketing application in an ICH region and until there are no pending or contemplated marketing applications in an ICH region, or at least 2 years have elapsed since the formal discontinuation of clinical development of the IP. If there is a country or institutional policy that specific records and documents be retained for a longer period than described above, the applicable sites must comply with those policies in addition to US and ICH policies.

No study records should be destroyed without prior written authorization from The Sponsor, if applicable. It is the responsibility of the Sponsor to inform the investigator when these documents no longer need to be retained.

14.4 Protocol Deviations

A protocol deviation is any noncompliance with the clinical trial protocol or GCP requirements. The noncompliance may be either on the part of the subject, the investigator, or the study site staff. As a result of deviations, corrective actions are to be developed by the site and implemented promptly.

It is the responsibility of the site to use continuous vigilance to identify and report deviations to the Sponsor Medical Monitor or designee as soon as protocol deviation is identified. All documentation regarding protocol deviations will be maintained in the regulatory file. All deviations must be addressed in study source documents and reported to the Sponsor. Protocol deviations must be sent to the local IRB/IEC per their guidelines. The site Principal Investigator is responsible for ensuring all study staff understands the local IRB/IEC reporting guidelines and adhere to all related requirements and documentation.

14.5 Publications and Data Sharing Policy

The Sponsor will comply with the requirements for publication of study results. In accordance with standard editorial and ethical practice, the Sponsor will generally support publication of multicenter studies only in their entirety and not as individual site data. In this case, a coordinating investigator will be designated by mutual agreement. Authorship will be determined by mutual agreement and in line with the International Committee of Medical Journal Editors authorship requirements.

16. APPENDICES

16.1 ECOG Performance Status Criteria

Grade	Description
0	Normal activity. Fully active, able to carry on all predisease performance without restriction
1	Symptoms but ambulatory. Restricted in physically strenuous activity, but ambulatory and able to carry out work of a light or sedentary nature (e.g., light housework, office work)
2	In bed < 50% of the time. Ambulatory and capable of all self-care, but unable to carry out any work activities. Up and about more than 50% of waking hours.
3	In bed > 50% of the time. Capable of only limited self-care, confined to bed or chair more than 50% of waking hours.
4	100% bedridden. Completely disabled. Cannot carry on any self-care. Totally confined to bed or chair.
5	Dead.

Source: Oken MM, Creech RH, Tormey DC, Horton J, Davis TE, McFadden ET et al. Toxicity and response criteria of the Eastern Cooperative Oncology Group. Am J Clin Oncol 1982; 5 (6):649-55.

16.2 Contraception Requirements

Definition of Female of Childbearing Potential (FCBP)

A female subject who is not sterile due to surgery (i.e., from bilateral tubal ligation/occlusion, bilateral oophorectomy, bilateral salpingectomy, or complete hysterectomy) or who does not have a congenital or acquired condition that prevents childbearing or who is not naturally postmenopausal for at least 12 consecutive months.

Definition of Female of Non-Reproductive Potential

Female subjects will be considered of non-reproductive potential if they:

1. Are postmenopausal if defined as amenorrheic for 12 consecutive months without an alternative medical cause. In women < 50 years of age and/or perimenopausal, a high follicle stimulating hormone (FSH) level in the postmenopausal range may be used to confirm a postmenopausal state in women not using hormonal contraception or hormonal replacement therapy. In the absence of 12 consecutive months of amenorrhea, a single FSH measurement is insufficient.

OR

2. Have had a hysterectomy and/or bilateral oophorectomy, bilateral salpingectomy, or bilateral tubal ligation/occlusion, at least 6 weeks prior to screening.

OR

3. Have a congenital or acquired condition that prevents childbearing.

Highly Effective Methods of Contraception (< 1% failure rate)

A highly effective method of contraception is defined as one that results in a low failure rate (i.e., less than 1% per year) when used consistently and correctly. For contraception, subjects should comply with one of the following:

1. Practice abstinence† from heterosexual activity

OR

2. Use (or have their partner use) acceptable contraception during heterosexual activity.

Acceptable methods of contraception are‡:

- Single method (one of the following is acceptable):
 - intrauterine device (IUD)
 - vasectomy of a female subject's male partner
 - contraceptive rod implanted into the skin

- Combination methods
 - Female subjects: the following hormonal contraceptive methods (stable dose at least 3 months prior to first dose of study treatment) may be used by female subjects and requires use of a male condom for the male partner:
 - oral contraceptive pill (estrogen/progestin pill or progestin-only pill)
 - subcutaneous contraceptive injection
 - contraceptive skin patches
 - vaginal contraceptive rings
 - contraceptive implants into skin

†Abstinence (relative to heterosexual activity) can be used as the sole method of contraception if it is: (1) consistently employed during the entire period of risk associated with the administered drugs; (2) consistent with the subject's preferred and usual lifestyle; and (3) considered acceptable by local regulatory agencies and IRBs/IECs. Periodic abstinence (e.g., calendar, ovulation, sympto-thermal, postovulation methods) and withdrawal are not acceptable methods of contraception.

‡If a contraceptive method listed above is restricted by local regulations/guidelines, then it does not qualify as an acceptable method of contraception for subjects participating at sites in this country/region.

Subjects should be informed that taking SL-172154, PLD, or MIRV may involve unknown risks to the fetus (unborn baby) if pregnancy were to occur during the study. To participate in the study, subjects of childbearing potential must adhere to the contraception requirement (described above) starting at least 14 days prior to the first dose of study treatment, during treatment, and through at least 6 months (or for the duration required by local regulatory guidance) after the last dose of PLD or at least 3 months after the last dose of MIRV or SL-172154, whichever is longer.

16.2.1 Pregnancy Status

In the rare event that beta-human chorionic gonadotropin (β -hCG) is elevated as a tumor marker, pregnancy should be excluded. At minimum, this requires obstetrics evaluation, serial β -hCG measurements and ultrasound to exclude pregnancy.

16.3 Cockcroft-Gault Formula for Creatinine Clearance

Creatinine clearance (mL/min)¹ = $\frac{Q \times (140 - \text{age [yr]}) \times \text{ideal body weight [kg]}^2}{72 \times \text{serum creatinine [mg/dL]}}$

Q = 0.85 for females

Q = 1.0 for males

OR

Creatinine clearance (mL/min)² = $\frac{K \times (140 - \text{age [yr]}) \times \text{ideal body weight [kg]}^1}{\text{serum creatinine } [\mu\text{mol/L}]}$

K = 1.0 for females

K = 1.23 for males

1. Creatinine clearance has a maximum value of 125 mL/min.

If a subject's actual body weight is less than his or her ideal body weight (IBW), then actual weight should be used. However, if the patient is obese, then a correction is used. If a subject's actual weight >30% his or her ideal body weight, then AIBW should be used in the Cockcroft-Gault equation. See Section 16.4 for calculation of AIBW and IBW.

Reference:

Winter M. Impact of Various Body Weights and Serum Creatinine Concentrations on the Bias and Accuracy of the Cockcroft-Gault Equation. *Pharmacotherapy: The Journal of Human Pharmacology and Drug Therapy*. 2012; 32:604-612.

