NOTE: Progression should be calculated from the date of the last administered dose of platinum therapy to the date of the radiographic imaging showing progression.

NOTE: Subjects who are platinum refractory during front-line treatment are excluded [primary platinum-refractory disease, defined as disease that did not respond to (CR or PR) or has progressed within \leq 3 months of the last dose of first-line platinum-containing chemotherapy].

8. **[MIRV Cohort]** Subjects must have received at least 1 but no more than 3 prior systemic lines of anticancer therapy.

Lines of therapy are defined in this study as:

- Adjuvant \pm neoadjuvant is considered 1 line of therapy.
- Maintenance therapy (e.g., bevacizumab, PARP inhibitors) will be considered part of the preceding line of therapy (i.e., not counted independently).
- Therapy changed due to toxicity in the absence of progression will be considered part of the same line (i.e., not counted independently).
- Hormonal therapy will be counted as a separate line of therapy unless it was given as maintenance.

9. **[MIRV Cohort]** Willing to provide an archival tumor tissue block or slides or undergo new biopsy using a low-risk, medically routine procedure for IHC confirmation of FR α positivity.

10. **[MIRV Cohort]** Subject's tumor must be positive for FR α expression defined as PS2+ \geq 25% by the Ventana FOLR1 Assay.

11. Eastern Cooperative Oncology Group Performance Status (ECOG PS) of 0 or 1.

12. Measurable disease by RECIST v1.1 using radiologic assessment.

13. Laboratory values must meet the following criteria.

Laboratory parameter	Threshold value
Absolute neutrophil count (ANC)	$\geq 1.5 \times 10^9/L$ without GCSF in prior 10 days or long-acting WBC growth factors in prior 20 days
Platelet count	$\geq 100 \times 10^9/L$ without platelet transfusion in prior 10 days
Hemoglobin (Hgb)	$> 9.0 \text{ g/dL}$ without packed RBC transfusion in the prior 7 days
Creatinine clearance (CrCl)	$\geq 30 \text{ mL/min}$ (using modified Cockcroft-Gault formula; Appendix Section 16.3)
ALT/AST	$\leq 3 \times \text{ULN}$
Total bilirubin	$\leq 1.5 \times \text{ULN}$; subjects with isolated indirect hyperbilirubinemia are permitted if direct bilirubin ratio is $< 35\%$ and total bilirubin is $\leq 3.0 \times \text{ULN}$
Serum albumin [MIRV cohort only]	$\geq 2 \text{ g/dL}$
Left ventricular ejection fraction (LVEF) [PLD Cohort only]	$> 50\%$ by ECHO/MUGA

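### The two unit versions of creatinine clearance in Protocol Appendix 16.3 disagree for women by about 4%, so the 30 mL/min entry limit depends on the laboratory's unit

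*Protocol*

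**What the plan says.** Criterion 13 in Protocol Section 4.1 sets a creatinine clearance of at least 30 mL/min and sends the reader to the appendix: "using modified Cockcroft-Gault formula; Appendix Section 16.3". Sections 4 and 6 rule out waivers. Chemistry is run at local laboratories (notes to the schedules in Sections 6.1 and 6.2).

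Appendix 16.3 offers two alternatives:

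- **Creatinine in mg/dL:** Q × (140 − age) × weight / (72 × creatinine), with "Q = 0.85 for females" and "Q = 1.0 for males".
- **Creatinine in µmol/L:** K × (140 − age) × weight / creatinine, with "K = 1.0 for females" and "K = 1.23 for males".

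Ideal body weight (IBW) is the default weight in both. Actual weight replaces it when lower. After a sentence saying that obese patients need a correction, the trigger for adjusted ideal body weight (AIBW) is written as "actual weight >30% his or her ideal body weight, then AIBW should be used in the Cockcroft-Gault equation".

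The hemoglobin line of criterion 13 reads at least 9.0 g/dL in the synopsis and above 9.0 g/dL in Section 4.1. Both continue "without packed RBC transfusion in the prior 7 days".

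**The concern.** The two versions are meant to be the same formula, with the unit conversion absorbed into the constant. The female-to-male ratio should then be equal in both. It is 0.85/1.0 = 0.85 in the mg/dL version and 1.0/1.23 = 0.813 in the µmol/L version, so the two cannot both hold.

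The female constant is the only one this trial needs. The tumours are ovarian, primary peritoneal and fallopian tube, and Appendix 16.4 gives an IBW formula for women only. By printing both versions, the protocol allows either to be used. At stake is whether an entry criterion that cannot be waived gives one answer for one patient.

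**Working it through.** **Inputs.** From Appendix 16.3: Q = 0.85 (female) and 1.0 (male), divisor 72, K = 1.0 (female) and 1.23 (male). From criterion 13: the limit of 30 mL/min. From Appendix 16.4: female IBW = 0.9 × height in cm − 92. Assumed, because the protocol does not give it: 1 mg/dL creatinine = 88.4 µmol/L.

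**Relation.** If c is the number of µmol/L per mg/dL, the two versions agree when K = Q × c / 72.

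**Male constant.** 1.0 × 88.4/72 = 1.228, which reproduces the printed 1.23.

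**Female constant.**

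- From the document alone: the male pair implies c = 1.23 × 72 = 88.56, so K = 0.85 × 88.56/72 = 0.85 × 1.23 = 1.0455.
- With c = 88.4: K = 0.85 × 88.4/72 = 1.0436.
- The printed 1.0 is not reproduced on either route.

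**Size of the disagreement.**

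| | c = 88.4 | c = 88.56 |
|---|---|---|
| µmol/L version relative to mg/dL version | 1/1.0436 − 1 = −4.2% | 1/1.0455 − 1 = −4.4% |
| mg/dL result when the µmol/L version gives 30 | 30 × 1.0436 = 31.3 | 30 × 1.0455 = 31.4 |
| µmol/L result when the mg/dL version gives 30 | 30/1.0436 = 28.7 | 30/1.0455 = 28.7 |

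**Illustration (assumed patient).** Age 70, height 160 cm, IBW = 0.9 × 160 − 92 = 52 kg, IBW used as the weight, creatinine 1.40 mg/dL = 1.40 × 88.4 = 123.76 µmol/L.

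- mg/dL version: 0.85 × 70 × 52 / (72 × 1.40) = 30.7 mL/min, eligible.
- µmol/L version: 1.0 × 70 × 52 / 123.76 = 29.4 mL/min, excluded.

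For this woman the mg/dL version reaches 30 at a creatinine of 0.85 × 70 × 52 / (72 × 30) = 1.43 mg/dL. The µmol/L version reaches it at 70 × 52/30 = 121.3 µmol/L, which is 1.37 mg/dL. The versions give different decisions only between those two values.

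**Weight rule.** Weight is the same multiplier in both versions, so it cancels from their ratio. Whatever the AIBW trigger is taken to mean, it adds nothing to the difference between units.

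**The case against.** The strongest reply is that the effect is trivial. It is about 1.3 mL/min at the limit, few women will be that close, and 1.0 may simply be 1.04 shortened. The error also excludes borderline women and does not admit women with poorer renal function. Eligibility deviations do not alter any analysis: neither Protocol Section 9.2.1 nor SAP Section 4 defines a per-protocol set, and SAP Section 6.2 only lists and summarises deviations. All of this stands as a limit on size. It does not remove the inconsistency, since the male constant beside it is given to two decimals and agrees with its mg/dL partner.

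Three stronger readings are tempting, and the documents do not support them.

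- **That the obesity wording also makes the limit depend on the unit.** It cannot, because weight enters both versions equally.
- **That AIBW applies to almost everyone.** Read literally, the trigger at an IBW of 52 kg is 0.3 × 52 = 15.6 kg. For weights from IBW up to 130% of IBW, that reading would raise clearance by up to 0.4 × 0.3 = 12%. The preceding sentence confines the correction to obese patients, and the literal reading would cancel both that sentence and the IBW default. The wording is loose, but a shift of this size should not be attributed to the plan.
- **That the hemoglobin criterion is left open.** Section 4 requires patients to meet the criteria as stated in Sections 4.1 and 4.2, so Section 4.1 governs. The synopsis differs from it only for a subject at exactly 9.0 g/dL.

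**Conclusion.** The point holds for the female constant. The two versions in Appendix 16.3 disagree for women by 4.2% to 4.4%, and the µmol/L version is the stricter, so its 30 mL/min limit corresponds to about 31.3 mL/min on the mg/dL scale. The inconsistency follows from the appendix's own figures. The outside conversion of 88.4 only refines the implied constant from 1.05 to 1.04.

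The practical consequence assumes that sites use the version matching their laboratory's unit and that the constant is printed correctly in the copy in use. That the population is female is inferred from the tumour types and the female-only IBW formula, because no sex criterion is written. The consequence is inconsistent exclusion of a few borderline women. Sample size, error rates and analysis sets are unaffected. The obesity wording and the hemoglobin inequality are separate editorial matters.

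**What to change.** Check the printed female K in Appendix 16.3 against the original document. If it is 1.0, restate it to agree with the mg/dL factor of 0.85 (about 1.04), so that both versions give the same clearance for the same woman.

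As separate minor edits:

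- Reconcile the AIBW trigger in 16.3 with the obesity sentence before it. The sponsor should confirm the intended trigger.
- Reconcile the hemoglobin inequality in the synopsis with that in Section 4.1, after checking both symbols in the original. Which threshold is clinically right is for the sponsor to settle.

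The cost is one constant and two wording changes in a clarification memo or the next amendment. No new data are needed, and nothing in the SAP has to change.
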